5.7. Interim monitoring and study stopping rules

An independent Data and Safety Monitoring Committee (DSMC) will be appointed to review the accumulating data and provide advice on whether the accumulating data from the trial justify continuing recruitment of further patients or further follow-up (see also section 8.7). The first review will take place after the first 6 patients (3 patients with intermediate risk disease and 3 metastatic patients) complete the study treatment and have reached the 24-week timepoint for efficacy assessment, unless there is a need to convene the Committee earlier due to the safety concerns. If a decision is made to continue the study, the DSMC will advise on the frequency of future reviews of the data on the basis of accrual and event rates.

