4.2.1 Vaccine formulation, storage and accountability

ChAdOx1.5T4

ChAdOx1.5T4 vaccine is an unlicensed medicinal product manufactured by the University of Oxford Clinical Biomanufacturing Facility (CBF), Churchill Hospital, Oxford. It is formulated in formulation buffer at a nominal concentration of 1.1×10^{11} vp/mL. The formulation buffer consists of 10mM Histidine, 7.5% sucrose, 35mM NaCl, 1mM MgCl₂, 0.1% PS80, 0.1mM EDTA, 0.5% EtOH, pH 6.6. The fill volume is 0.5-1.0 mL. The dose of ChAdOx1.5T4 to be used in this study is 2.5×10^{10} vp. It is manufactured, labelled and released under Good Manufacturing Practice conditions to the clinical sites by the CBF. All movements of the study vaccine between the CBF and the clinical sites will be documented. The vaccine is supplied as liquid in glass vials and is stored at -80C in a locked, alarmed, temperature monitored freezer prior to release to the clinical sites. Following shipment to sites, the vaccine is stored as above, however, short-term storage for up to 3 months at 2-8C is acceptable if required, based on the manufacturer's stability data to date.

MVA.5T4

MVA.5T4 vaccine is an unlicensed medicinal product that has not been administered to humans before. VANCE01 trial has made use of the biologically equivalent MVA.5T4 vaccine supplied by Oxford BioMedica (manufactured by Baxter), trade name TroVax®. The new batch of MVA.5T4

vaccine expresses the 5T4 antigen under control of the different poxvirus promoter. It has been manufactured under Good Manufacturing Practice conditions by IDT Biologika GmbH, Germany. MVA.5T4 is supplied as a frozen liquid formulation in 10mM Tris buffer 140 mM NaCl, pH 7.7 in 2.0 mL clear glass vials. The formulation titre is 2×10^9 pfu/ml, the final drug product titre is 1×10^9 pfu/ml. The fill volume is 0.55 mL. Further details relating to batch manufacture can be found in the MVA.5T4 IMPD.

To ensure consistency with the VANCE01 clinical trial and all previous University of Oxford trials using MVA vectored vaccines, the dose to be used in this study will be 2×10^8 pfu. The vaccine will be labelled and released under Good Manufacturing Practice conditions to the clinical sites by the CBF. All movements of the study vaccine between the CBF and the clinical sites will be documented. At CBF it is stored at -80C in a locked, alarmed, temperature monitored freezer prior to release to the clinical sites. Following shipment to sites, the vaccine is stored as above.

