5. RECRUITMENT AND WITHDRAWAL OF STUDY SUBJECTS

5.1. Selection of Participants

Participants will be recruited into either of two cohorts within the study - subjects with operable localised or locally advanced prostate cancer who are planned to undergo radical prostatectomy, or subjects with metastatic prostate cancer who demonstrate disease progression on therapy with second generation anti-androgens (enzalutamide or abiraterone).

Radical prostatectomy group

The subjects recruited will be men over the age of 18 years, diagnosed with low- or intermediate-risk localised or locally advanced prostate cancer and deemed operable and fit to undergo radical prostatectomy by the treating consultant urological surgeon. The number of subjects newly diagnosed with low- and intermediate-risk prostate cancer and selecting radical prostatectomy as their treatment option at the Oxford Churchill Hospital is approximately 5 per month. At the point when the decision has been made to offer radical prostatectomy as one of the potential treatment options, the trial will be introduced to the patient by the existing medical care team during their routine clinic visit, the PIS will be given and permission will be sought for the research team to approach them.

Metastatic prostate cancer groups

Subjects recruited will be men over the age of 18 with a diagnosis of prostate cancer, metastatic to one or more distant sites, who have demonstrated disease progression following anti-androgen treatment with either enzalutamide or abiraterone as a standard of care. Subjects will be identified in the outpatient setting by the existing medical care team during their routine clinic visit, the PIS will be given and permission sought for the research team to approach them. The number of metastatic prostate cancer patients demonstrating evidence of disease progression on enzalutamide is approximately 2 per month at the Oxford Churchill Hospital.

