
8. SAFETY ASSESSMENT

8.1. Specification, timing and recording of safety parameters

At regular intervals (specified in section 6.1), the subjects will be assessed for the following safety parameters:

- General physical examination and vital signs
- Full blood count
- Urea and electrolytes
- Liver function tests
- Kidney function tests

The above will be recorded in the patients' case report form (CRF) by the relevant clinician or their nominee.

Reports of recorded events, along with a narrative from the Chief Investigator, will be submitted to the Safety Monitoring Committee after every 6 completed patients.

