8.7. Data and Safety Monitoring Committee

A Data and Safety Monitoring Committee (DSMC) will be appointed to provide real-time safety oversight. It will consist of a consultant oncologist, a consultant physician with experience of vectored vaccine trials, a further member with statistical expertise and up to two further members with trial expertise, all of them independent of the study. The DSMC will review all SAEs at the meetings that will be convened following each interim safety report and a narrative from the Chief Investigator at the timepoints as below:

An interim safety report of all recorded events, along with a narrative from the Chief Investigator, will be submitted to the Data and Safety Monitoring Committee for review after the first 6 patients (3 patients with intermediate risk disease and 3 metastatic patients) complete the study treatment and have reached the 24-week timepoint for efficacy assessment. An updated report to the Data and Safety Monitoring Committee, covering all enrolled participants to date will then be triggered when every 6th subsequent participant has reached 24-week timepoint for efficacy assessment.

The DSCM has the power to terminate the study if deemed necessary following a study-related SAE.

The DSMC chair will be notified of SAEs if deemed possibly, probably or definitely related to study-related interventions within 24 hours of the investigators' being aware of their occurrence.

The chair of the DSMC will be contacted for advice and independent review in the following situations:

- Following any SAE deemed to be possibly, probably, or definitely related to the study vaccine.
- Any other situation where the Investigator feels independent advice or review is important.

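### No aggregate DSMC safety review is scheduled in Sections 5.7 and 8.7 before week 24, by which time Group 1 may be fully enrolled and dosed, and Section 8.1 gives a different trigger

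*Protocol*

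**What the plan says.** Section 5.7 places the first DSMC review "after the first 6 patients (3 patients with intermediate risk disease and 3 metastatic patients) complete the study treatment" and those men "have reached the 24-week timepoint for efficacy assessment, unless there is a need to convene the Committee earlier" because of safety concerns. It gives the committee the task of advising whether recruitment should continue, and leaves the frequency of later reviews to the committee.

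Section 8.7 repeats the 3+3 condition for the interim safety report, but fixes the later cadence: an updated report is "triggered when every 6th subsequent participant has reached 24-week timepoint for efficacy assessment". Section 8.1 gives another rule again: reports "will be submitted to the Safety Monitoring Committee after every 6 completed patients", with no split by group and no week 24.

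Section 8.7 also provides oversight between scheduled reports. The DSMC chair is told within 24 hours of SAEs judged related to study interventions. The chair is contacted for independent review after an SAE possibly, probably or "definitely related to the study vaccine", and whenever the investigator thinks independent advice is important. The committee can terminate the study after a study-related SAE.

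Sections 4.3 and 6.1 end Group 1 dosing at week 1 (Day 7). Section 7.1 defines the Group 1 PSA endpoint as rate of change before prostatectomy, which Appendix 1 places from week 5. The 24-week response definitions in Section 7.1 apply to metastatic men only.

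**The concern.** Safety is a co-primary objective in both groups, yet the scheduled safety report waits for an efficacy time-point. In Group 1 that time-point is the last visit (V6), some 23 weeks after the last dose. A Group 1 man has no study dose left after Day 7, so aggregate review can help only men not yet enrolled. If the cohort has closed by then, the committee's advice on continuing recruitment comes too late for it.

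The protocol's own background makes an early look relevant. Section 4.2.1 says the "MVA.5T4 vaccine is an unlicensed medicinal product that has not been administered to humans before". Section 2.5 reports that systemic reactions in VANCE01 were most marked after the MVA boost in the accelerated schedule. Group 1 uses that one-week interval and adds nivolumab on the same day.

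The inconsistent triggers matter whatever the accrual rate, because the sites and the committee cannot tell when a report is due.

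**Working it through.** **Inputs.** Group sizes 12 and 24 (Section 4.3). Monthly pools at one centre: "selecting radical prostatectomy as their treatment option at the Oxford Churchill Hospital is approximately 5 per month" for Group 1, and about 2 per month progressing on enzalutamide for Group 2 (Section 5.1). Uptake u, the share of the pool that enrols, is not stated and is varied here. One month = 30.44 days, so 1 week = 0.23, 5 weeks = 1.15 and 24 weeks = 5.52 months.

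**The plan's own figure.** Group 2 accrual plus follow-up = 24/2 + 12 = 24 months, which matches the planned study period of about 2 years in the Synopsis. So 2 per month is at least consistent with the planning. No such check is available for the Group 1 figure.

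**Timing at a common uptake u.**
- 12th Group 1 man enrolled: 12/(5u); last dosed 0.23 months later.
- First scheduled review: max[3/(5u), 3/(2u)] + 5.52 = 3/(2u) + 5.52.
- Group 2 men enrolled by then: 2u × review time, in whole men.

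| Uptake | 12th Group 1 man enrolled (months) | Last Group 1 dose (months) | First review (months) | Group 1 enrolled at review | Group 2 enrolled at review |
|---|---|---|---|---|---|
| 100% | 2.40 | 2.63 | 7.02 | 12 | 14 |
| 50% | 4.80 | 5.03 | 8.52 | 12 | 8 |
| 25% | 9.60 | 9.83 | 11.52 | 12 | 5 |
| 20% | 12.00 | 12.23 | 13.02 | 12 | 5 |
| 15% | 16.00 | 16.23 | 15.52 | 11 | 4 |

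**Is Group 2 accrual the cause?** Not mainly. On the Group 1 clock alone, at 5 per month, the third man reaches week 24 at 3/5 + 5.52 = 6.12 months, still well after 2.63.

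**Break-even.**
- Common uptake: 12/(5u) + 0.23 = 3/(2u) + 5.52, so 0.9/u = 5.29 and u = 0.17.
- Group 2 fixed at 2 per month, Group 1 at r per month: near break-even the third Group 1 man is the later one, so 12/r + 0.23 = 3/r + 5.52. This gives 9/r = 5.29 and r = 1.70, or 34% of the pool.
- Below break-even, with Group 1 at 30% (1.5 per month) and Group 2 at 2 per month: review at 3/1.5 + 5.52 = 7.52 months, last Group 1 dose at 12/1.5 + 0.23 = 8.23 months, and 11 of 12 enrolled at the review.

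**Early look.** Group 1 V4 is at week 5, so the third man passes it at 3/(5u) + 1.15 months. Enrolled by then: 3 + 5u × 1.15 = 8.75, 5.9 or 4.4 at 100%, 50% or 25% uptake, that is about 9, 6 or 4 of 12. In Group 2 the visit after the first nivolumab is also at week 5: 3 + 2u × 1.15 = 5.3, 4.2 or 3.6 of 24.

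**What the Section 8.1 rule could mean.** If completed means end of follow-up, that is 6 months in Group 1 and 12 months in Group 2 (Section 4.4). If it means end of treatment, six Group 1 men qualify at 6/5 + 0.23 = 1.43 months at the full pool rate. The second reading would produce a report more than five months before the 7.02 months of Sections 5.7 and 8.7.

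**The case against.** The strongest reply is that independent oversight does not wait for week 24. Section 5.7 lets the committee meet early for safety concerns, with no restriction to SAEs. Section 8.7 gives 24-hour notice of SAEs related to any study intervention, and the investigator's route to the chair is open-ended. Section 8.5 sends all SAEs to the Study Medical Monitor within 24 hours, and any hospitalisation counts as an SAE. This stands. A reader might infer that Group 1 is treated before any independent safety review, or that the early routes cover only single related SAEs. The documents support neither. What remains is that these routes need an event or a judgement to set them off. A grade 3 event that is not an SAE, or an accumulation of milder ones, need not reach the committee.

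Second, a reader might take 12 of 12 as a fact from the protocol. It is not. The Section 5.1 figures count one centre's patients before eligibility and consent, and accrual at the second centre is not stated. The result depends on assumed uptake.

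Third, the novelty of the product is limited. Section 4.2.1 calls the MVA used in VANCE01 biologically equivalent. Section 2.2 says the transgene insert is the same and the promoter differs. Section 2.4 records over 600 patients given the earlier product. This weakens the urgency, but that experience did not include nivolumab given with this vaccine.

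Fourth, a V4 look comes only about 0.9 months after the single infusion, whereas the median onsets in Table 1 run from 1.4 to 3.3 months under continuous dosing. That is a fair limit on what an early look can show.

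**Conclusion.** The point holds as one about scheduled aggregate review. Sections 5.7 and 8.7 set none before week 24, and the wait does not serve the Group 1 primary PSA endpoint. With the single-centre pools standing in for accrual, the last Group 1 dose precedes the first scheduled review by about 4.4, 3.5 or 1.7 months at 100%, 50% or 25% common uptake. The ordering reverses below about 17% common uptake, or below about 1.7 Group 1 men per month with Group 2 at 2 per month. Just below those limits most of Group 1 is still enrolled by the review (11 of 12 in both cases worked).

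The conflict between Sections 5.7, 8.1 and 8.7 over when reports are due rests on no assumption. Nor does the wording that counts only intermediate-risk Group 1 men when low-risk men also enrol, or the chair's SAE review item that names only the vaccine while the notification sentence covers all study interventions.

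This should be changed because the remedy is cheap. It does not show that participants are without independent oversight.

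**What to change.** 1. State one trigger and one cadence, in the same words, in Sections 5.7, 8.1 and 8.7. Define completed, and say whether the later frequency is fixed or set by the DSMC.
2. Count low- as well as intermediate-risk Group 1 men towards the trigger.
3. Add a scheduled safety-only DSMC report when the first 3 Group 1 men have completed V4, and another when the first 3 Group 2 men have completed the visit after their first nivolumab. Include non-serious and grade 3 events. Keep the week-24 review.
4. In Section 8.7, align the chair's SAE review item with the notification sentence, so that both cover all study interventions.

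The cost is one or two extra DSMC teleconferences on data already collected at scheduled visits. No recruitment pause is implied, so men enrolled while the report is being prepared are not covered by it. The early look captures early reactogenicity and infusion events. It will miss later-onset immune toxicity, which the week-24 review still covers.

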6. TREATMENT OF STUDY SUBJECTS

6.1. Study visits

The study visits and administration of investigational therapies will be undertaken by an adequately qualified and trained member of the team of investigators. Each visit is assigned a time point and a window period, within which the visit will be conducted. These can be found in the schedule of attendances (Appendix 1).

Screening visit

All potential participants will have a screening visit, which may take place up to 4 weeks prior to the first study procedure. Informed consent will be taken at screening prior to any study-specific procedures being carried out, as described in section 5.2. If consent is obtained, the screening procedures indicated in the schedule of attendances will be undertaken. A baseline medical history, physical examination and assessment of performance status will be performed. Vital signs will be recorded and urinalysis will be performed. Inclusion and exclusion criteria will be checked. Blood will be drawn for clinical haematology and biochemistry, HIV, Hepatitis B and Hepatitis C serology, PSA, exploratory biochemistry and ctDNA. Subjects will be counseled by one of the investigators prior to HIV, Hepatitis B and Hepatitis C testing.

Potential subjects will be informed that blood samples, as well as the surgical specimens from radical prostatectomy and archival biopsy samples that are collected as standard of care or newly obtained on-study tumour biopsy samples will be used for research purposes. They will be informed that after study investigations are completed, any surplus samples of blood (and/or surgical or biopsy material) may be stored for possible future ethically approved research,

including for example exploratory immunology, and genotypic testing of genetic polymorphisms potentially relevant to vaccine immunogenicity. Subjects will be able to decide if they permit such future use of any unused or surplus samples. If a subject elects not to permit this, all of that subject's leftover samples will be discarded at the end of the study to meet Good Clinical Practice (GCP) and regulatory requirements.

The eligibility of the subject will be reviewed at the end of the screening visit and again when all results from the screening visit have been considered. If eligible, a week 0 enrolment visit will then be scheduled.

Subsequent Visits

At each subsequent study visit the ongoing eligibility of the volunteer will be reviewed. Vital signs will be recorded, urinalysis performed, ECOG performance status assessed and if necessary, a medical history and physical examination may be undertaken to determine any relevant interval changes in the participants health. In the event of new clinical or laboratory findings, study procedures involving administration of investigational vaccines or intravenous checkpoint inhibitors may be postponed according to criteria in Section 5.5. All blood tests should be taken prior to administration of any study therapies.

Group 1

Day 0: Enrolment, ChAdOx1.5T4 priming vaccination visit

Subjects will not be considered enrolled in the study until they have received the first study vaccination with ChAdOx1.5T4 on Day 0. Prior to vaccination, blood tests will be taken as detailed in the schedule of attendances (Appendix 1). Following intramuscular administration of the ChAdOx1.5T4 vaccine, the injection site will be covered with a sterile dressing and the patient will stay under observation, in case of immediate adverse events. Observations will be taken 60±15 min after vaccination and the sterile dressing removed and injection site inspected. A diary card, oral thermometer and tape measure will be given to each participant to solicit the following adverse events:

- Localised adverse events
 - o Diameter of redness at vaccination site
 - o Diameter of swelling at vaccination site
 - o Pain, warmth and erythema at the vaccination site

- Systemic adverse events
 - o Recorded temperature and pyrexial episodes
 - o Feverishness
 - o Headaches
 - o Fatigue
 - o Nausea
 - o Generalised muscle aches

- o Generalised joint aches

Day 7: MVA.5T4 boost vaccination visit and first checkpoint inhibitor therapy

- Prior to Day 7 study vaccination and checkpoint inhibitor therapy, the subject's diary card entries will be reviewed and any adverse events assessed. Blood tests will be taken as detailed in the schedule of attendances (Appendix 1). The MVA.5T4 vaccine will be administered intramuscularly and the injection site(s) will be covered with a sterile dressing. The participants will remain under observation and vital signs repeated 60 ± 15 min after vaccination when the sterile dressing will be removed and injection site inspected. Participants will then undergo intravenous cannulation and intravenous infusion of nivolumab. The infusion will preferably commence a minimum of 60 minutes following administration of the MVA.5T4 vaccine, but if operationally required simply on the same day as immunisation. Participants will remain in the department for a further 30 ± 15 minutes on completion of the infusion and vital signs repeated prior to departure. At the conclusion of this visit, the intravenous canula will be removed.

Participants will be provided with an alert card, in line with the manufacturer's guidance, outlining the 'red flag' symptoms of immune-mediated checkpoint inhibitor toxicity and emergency contact details for the study medical team. An oral thermometer (if necessary) and new diary card will be given to each participant. In addition to the local and systemic AEs listed above, checkpoint inhibitor associated AEs will also be solicited in the following organ systems:

- Respiratory
- Dermatological
- Gastrointestinal
- Urological

Group 2

Day 0: Enrolment, ChAdOx1.5T4 priming vaccination visit

Subjects will not be considered enrolled in the study until they have received the first study vaccination with ChAdOx1.5T4 on Day 0. Prior to vaccination, blood tests will be taken as detailed in the schedule of attendances (Appendix 1). Following intramuscular administration of the ChAdOx1.5T4 vaccine, the injection site will be covered with a sterile dressing and the patient will stay under observation, in case of immediate adverse events. Observations will be taken 60 ± 15 min after vaccination and the sterile dressing removed and injection site inspected. A diary card, oral thermometer and tape measure will be given to each participant to solicit the following adverse events:

- Localised adverse events
 - o Diameter of redness at vaccination site
 - o Diameter of swelling at vaccination site

- o Pain, warmth and erythema at the vaccination site
- Systemic adverse events
 - o Recorded temperature and pyrexial episodes
 - o Feverishness
 - o Headaches
 - o Fatigue
 - o Nausea
 - o Generalised muscle aches
 - o Generalised joint aches

Week 4: MVA.5T4 boost vaccination visit and first checkpoint inhibitor therapy

Prior to Week 4 study vaccination and checkpoint inhibitor therapy, the subject's diary card entries will be reviewed and any adverse events assessed. Blood tests will be taken as detailed in the schedule of attendances (Appendix 1). The MVA.5T4 vaccine will be administered intramuscularly and the injection site(s) will be covered with a sterile dressing. The participants will remain under observation and vital signs repeated 60 ± 15 min after vaccination when the sterile dressing will be removed and injection site inspected. Participants will then undergo intravenous cannulation and intravenous infusion of nivolumab. The infusion will preferably commence a minimum of 60 minutes following administration of the MVA.5T4 vaccine, but if operationally required simply on the same day as immunisation. Participants will remain in the department for a further 30 ± 15 minutes on completion of the infusion and vital signs repeated prior to departure. At the conclusion of this visit, the intravenous canula will be removed and participants will be provided with an alert card, in line with the manufacturer's guidance, outlining the 'red flag' symptoms of immune-mediated checkpoint inhibitor toxicity and emergency contact details for the study medical team. In addition to the local and systemic AEs listed above, checkpoint inhibitor associated AEs will also be solicited in the following organ systems:

- Respiratory
- Dermatological
- Gastrointestinal
- Urological

Week 8: Second checkpoint inhibitor therapy

Prior to Week 8, blood tests will be taken as detailed in the schedule of attendances (Appendix 1). The results of clinical haematology and biochemistry (excluding serum PSA and thyroid function tests) taken either on arrival or within the preceding 48 hours will be reviewed prior to proceeding with checkpoint inhibitor therapy. Participants will undergo intravenous cannulation and intravenous infusion of nivolumab following the same administration and monitoring plan as on Week 4.

Week 12: Second cycle of ChAd-MVA immunisation – ChAdOx1.5T4 boost and third checkpoint inhibitor therapy

Prior to week 12, the subject's diary card entries will be reviewed and any adverse events assessed. Blood tests will be taken as detailed in the schedule of attendances (Appendix 1). The results of clinical haematology and biochemistry (excluding serum PSA and thyroid function tests) taken either on arrival or within the preceding 48 hours will be reviewed prior to administration of vaccine. Then the patients will undergo ChAdOx1.5T4 vaccination and nivolumab infusion, following the same administration and monitoring plan as on Week 4.

Week 16: Second cycle of ChAd-MVA immunisation – MVA.5T4 boost

Prior to week 16, the subject's diary card entries will be reviewed and any adverse events assessed. Blood tests will be taken as detailed in the schedule of attendances (Appendix 1). The results of clinical haematology and biochemistry (excluding serum PSA and thyroid function tests) taken either on arrival or within the preceding 48 hours will be reviewed prior to administration of vaccine. Then the patients will undergo MVA.5T4 vaccination, following the same administration and monitoring plan as on Day 0.

All remaining visits – groups 1 and 2

At all remaining follow up visits, blood tests will be taken as detailed in the schedule of attendances (Appendix 1). Vital signs will be recorded, urinalysis performed, ECOG performance status assessed and if necessary, a medical history and physical examination may be undertaken to determine any relevant interval changes in the participants health. Subjects are recommended to carry their clinical trial alert card, outlining the 'red flag' symptoms of immune-mediated checkpoint inhibitor toxicity and emergency contact details for the study medical team, for a minimum of 6 months after treatment on study.

Telephone communications

Patients will be telephoned by a research nurses on day 2-5 (48-120 hours) following vaccination and/or checkpoint inhibitor therapy to enquire about adverse events and provide further advice regarding completion of the diary card.

